9.5.16.3. Cumulative Prednisone Dose

Cumulative SLE-related prednisone dose (area under the curve [AUC]) is defined as the sum of daily prednisone dose from Day 1 to the Week 52 study completion date, considering only corticosteroids used to treat SLE. Missing values will be imputed for each day following the last visit day up to the scheduled Week 52 visit date (treatment start date + 52 * 7) for subjects who die or withdraw. The daily prednisone dose up to Week 52 after the last visit day, if prior to Week 52 visit date (i.e. for subjects who withdraw from the study or die), will be imputed using the average of the last 28 daily

prednisone doses prior to the day of last visit. For subjects who withdraw from study or die before Day 27, the daily prednisone dose up to Week 52 after early withdrawal or death will be imputed using the average post-baseline daily doses available prior to withdrawal or death.

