9.5.16. Prednisone

All prednisone analyses and summaries will consider SLE-related steroids only but data will also be derived for all indications steroids (SLE and non-SLE) for reference where indicated below.

The following will apply to all derivations in this section unless otherwise stated:

- For steroid use analyses, all steroid dosages are converted to a prednisone equivalent in milligrams; therefore, analyses refer to average daily prednisone dose instead of average daily steroid dose. See [Appendix 4: Prednisone Equivalent Conversion](#) for instructions on converting steroids to prednisone equivalents.
- This appendix will be updated throughout the course of the study to include all corticosteroids taken by subjects and will be finalized prior to the first database release and unblinding.
- For all derivations of the average daily prednisone equivalent dose including baseline, days on which a subject does not have prednisone use recorded will be considered as 0 mg for the day.
- Steroids taken intravenously (IV), intramuscularly (IM), subcutaneously (SC), intradermally, and orally are considered in prednisone dose derivations only.
- All steroids taken on any given day, including overlaps, will be accounted for in calculations of average daily prednisone dose. To achieve this programmatically, each entry is converted to the prednisone equivalent daily dose (see [Appendix 4: Prednisone Equivalent Conversion](#)) and the sum of the prednisone equivalent doses on Day X gives the total prednisone equivalent daily dose on Day X. For example, if two steroids are given on the same day they will be converted to a prednisone equivalent daily dose and then added together to achieve a total for that day.

Steroids used to treat SLE are those with medication type corticosteroid for SLE (SDTM.CM.CMCAT = 'CORTICOSTEROID FOR SYSTEMIC LUPUS ERYTHEMATOSUS').

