12.1. Major Efficacy Analyses

12.1.1. Percent of Subjects with Prednisone Reduction by $\geq 25\%$ from baseline to ≤ 7.5 mg/day during Week 40 through Week 52

Primary Analysis

For this analysis, only steroids used to treat SLE will be included and only subjects with a baseline average daily prednisone dose >7.5 mg/day will be included. See Section 9.5.16.1 for derivation of baseline prednisone dose and Section 9.5.16.2 for derivation of average prednisone use between Week 40 to Week 52.

The percent of subjects whose average prednisone dose has been reduced by $\geq 25\%$ from baseline to ≤ 7.5 mg/day during Weeks 40 through 52 will be compared between belimumab and placebo using a logistic regression model. Independent variables in the model will include treatment group, baseline prednisone dose, and the following

randomization stratification factors per the eCRF: screening SELENA SLEDAI score (≤ 9 vs. ≥ 10), and region. A responder is defined as having a prednisone reduction by $\geq 25\%$ from baseline to ≤ 7.5 mg/day during Weeks 40 through 52.

Any subject who withdraws from the study or adds new immunomodulatory agents used to treat SLE (note that this will include switches) prior to the Week 52 visit will be considered having no steroid reduction.

A summary of the number and percentage of subjects who are responders by treatment group, the treatment difference versus placebo, the odds ratio and 95% CI versus placebo, and a p-value for the odds ratio will also be provided.

Sensitivity Analysis

- To examine the robustness of the results, a sensitivity analysis of the SLE-related steroid reduction will be performed without considering any information related to the use of new immunomodulatory agents (note that this will include switches).

Additional Summaries of Prednisone

- A summary of the number and percentage of subjects with average SLE-related daily prednisone dose ≤ 7.5 mg/day and > 7.5 mg/day at baseline (Day 1) and treatment completion date will be presented for treatment completers.
- The cumulative SLE-related prednisone dose will be derived as described in Section 9.5.16.3. A table of descriptive statistics will be presented including the mean, standard deviation, median, 25th and 75th percentiles, minimum and maximum.
- A listing of cumulative SLE-related prednisone dose will be displayed by treatment and subject.

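### Cumulative prednisone dose goes on accruing after death, and no observed-dose figure is planned beside the imputed 52-week total

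*SAP*

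**What the plan says.** All references are to the Week 52 RAP in the SAP unless stated.

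- **Who and which days (9.5.16.3).** "Missing values will be imputed for each day following the last visit day up to the scheduled Week 52 visit date". The end date and the subjects concerned are given together: "treatment start date + 52 * 7) for subjects who die or withdraw". A later sentence in the same section names the group again: "i.e. for subjects who withdraw from the study or die".
- **What value.** The daily dose on those days "will be imputed using the average of the last 28 daily" values, the window being the "prednisone doses prior to the day of last visit".
- **Very early leavers.** "For subjects who withdraw from study or die before Day 27", a separate average applies, built from whatever post-baseline days exist before withdrawal or death. This too is carried to Week 52.
- **Which steroids (9.5.16).** "Steroids taken intravenously (IV), intramuscularly (IM), subcutaneously (SC), intradermally, and orally are considered in prednisone dose derivations only". No cap and no exclusion of pulses is stated.
- **Where it is used (12.1.1, additional summaries).** "The cumulative SLE-related prednisone dose will be derived as described in Section 9.5.16.3". It feeds one descriptive table (mean, SD, median, quartiles, minimum, maximum) and one listing by subject. There is no model, confidence interval or p-value.
- **The neighbouring rule (9.5.16.2).** The Weeks 40–52 average for a subject who leaves after the Week 40 visit runs only to withdrawal or death, whichever comes first.

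**The concern.** For a subject who withdraws alive, dose after the last visit is unknown, and filling it in is an assumption that can be debated. For a subject who has died, no dose exists. Giving that subject steroid until Study Day 365 records treatment that could not have been taken, and it does so in a by-subject listing as well as in the summary table. The RAP does the opposite one section earlier and gives no reason for the difference.

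For withdrawals, the filled-in value is a 28-day mean that includes intravenous and intramuscular doses. A short course of high dose inside that window is therefore counted again for each further 28 days filled. The only prednisone sensitivity analysis in 12.1.1 concerns new immunomodulatory agents, so nothing planned would show a reader how much of a total was observed and how much was imputed. This is the only planned summary of total steroid dose.

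**Working it through.** The plan states no figure for cumulative dose, so there is none to reproduce.

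**Inputs from the documents.** Imputation ends at treatment start + 52 × 7 = +364 days, which is Study Day 365 (9.5.16.3, 9.5.2). The Week 12, 24, 36 and 48 visits fall on Days 85, 169, 253 and 337 (9.5.3). Methylprednisolone converts at 1.25 (Appendix 4). Planning mortality is 0.564% with 4,000 subjects randomized 1:1, so 2,000 per arm (5.1).

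**Assumed inputs.** Background dose, pulse size, day of leaving and withdrawal proportion. The documents give none of these.

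**1. Days filled.** 365 − last visit day gives 280, 196, 112 and 28 days for the four visits above.

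**2. One death.** Assume 20 mg/day and a death on the day of the Week 24 visit: 20 × 196 = 3,920 mg counted after death. At 10 mg/day it is 1,960 mg.

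**3. Effect of deaths on an arm mean.** Expected deaths: 0.00564 × 2,000 = 11.28. With death at mid-year (182 days left):
- 10 mg/day: 11.28 × 10 × 182 / 2,000 = 10.3 mg
- 20 mg/day: 11.28 × 20 × 182 / 2,000 = 20.5 mg

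Against an assumed year at 10 mg/day (3,650 mg), these are about 0.3% and 0.6%.

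**4. A pulse inside the window.** Its total is spread over 28 days, then repeated (365 − last visit day)/28 times: 10, 7, 4 or 1 further times for the four visits. Illustration with 10 mg/day and a last visit on Day 169:

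| Pulse (mg prednisone equivalent) | Imputed mg/day | Observed total (mg) | Total under the rule (mg) | Ratio |
|---|---|---|---|---|
| 937.5 | 43.5 | 2,628 | 11,150 | 4.2 |
| 1,875 | 77.0 | 3,565 | 18,650 | 5.2 |
| 3,750 (3 × 1,000 × 1.25) | 143.9 | 5,440 | 33,650 | 6.2 |

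For the last row: 10 + 3,750/28 = 143.9 mg/day; 143.9 × 196 = 28,210 mg filled; 169 × 10 + 3,750 = 5,440 mg observed. Over backgrounds of 5–20 mg/day and last visits from Day 85 to Day 337, the ratio for these pulses runs from 1.2 to 10.3. In the last row the repeated pulse is 7 × 3,750 = 26,250 mg, so each such subject moves a 2,000-subject mean by 13.1 mg.

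**5. Withdrawals without a pulse.** Mean shift = proportion × dose × 182 days. At 5% and 10 mg/day it is 91 mg; at 20% and 20 mg/day it is 728 mg. This shows only how wide the possible range is.

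**6. What a per-day figure does.** For the 3,750 mg pulse with a last visit on Day 169: 5,440/169 = 32 mg/day observed, against 33,650/365 = 92 mg/day under the rule. With a last visit on Day 29: 4,040/29 = 139 mg/day, against (4,040 + 336 × 143.9)/365 = 144 mg/day.

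**The case against.** The strongest reply is that this is one descriptive table and one listing. Cumulative dose is not an endpoint in protocol 8.5.3 or RAP 2.2.2. The objective is steroid reduction during Weeks 40–52, and the responder analysis in 12.1.1 serves it; that analysis counts study withdrawals as no reduction and does not use this variable. The table also reports the median and quartiles, which a few extreme totals barely move. Carrying dose forward for a subject who withdraws alive is disclosed and prespecified, and preferring another convention is a matter of taste. All of this stands. It limits the point to deaths and to the missing observed-dose display.

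Three stronger inferences are tempting, and the documents do not support them.

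- **That subjects leave during flares, so the rule repeats flare doses.** No passage says so. The rule is triggered by leaving the study or dying, not by stopping study agent. A subject who needs a prohibited drug stops study agent but stays on study to Week 52 (protocol 5.5.1, 6.5), so observed doses are used.
- **That any pulse just before leaving is repeated.** The 28-day window ends before the last visit. A pulse between that visit and death or withdrawal lies outside it. Subjects leaving before Day 27 follow the separate average.
- **That the arm means will shift by some stated percentage, or the arm difference will be biased.** Either would need the frequency, size and timing of pulses and the withdrawal rate by arm.

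The reply does not reach the days after death. No assumption about missing data makes those doses real.

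**Conclusion.** The point holds in a limited form and is minor. The RAP counts steroid after death in a table and a listing, against its own practice in 9.5.16.2. The effect on an arm mean is small under the planning mortality, mid-year deaths and 10–20 mg/day, while the error in an individual listed total can be large. For withdrawals, the rule can multiply a pulse in the window several times, but how often that would happen cannot be judged from the documents. What is missing there is a display that lets a reader see it. The conclusions on mortality, AESI and steroid reduction are not affected.

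**What to change.** 1. Impute no dose after death. This should also apply to a subject who withdraws and is later found to have died before Week 52, using the date of death as derived in 9.1.1.
2. Keep the prespecified 52-week imputed total for subjects who withdraw alive.
3. Beside it, show the observed dose to the earliest of death, withdrawal or completion, both as a total and per day observed. State the imputation rule in a footnote to the table and the listing.
4. In the same footnote, say how two uncovered cases were handled. One is doses recorded after the last visit but before withdrawal or death, which imputation might replace. The other is a subject who leaves on or after Day 27 with a last visit before Day 29, and so has fewer than 28 post-baseline days in the window.

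The cost is one changed derivation and a few added columns. Totals cut off at death are lower and must be read with the per-day figure. The per-day figure dilutes a pulse but does not remove it when follow-up is short, as the Day 29 case in the working shows. The Years 2–5 RAP (Section 1) records that the Week 52 data were unblinded on 2-JAN-2019 and have been reported, so this should be labelled a post hoc supplementary display.

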9.5.17. Immunomodulatory Medications

Immunomodulatory medications are identified as all immunosuppressants with ATC code beginning “L04A” plus cyclophosphamide and mercaptopurine. For further detail see [Appendix 3](#): SLE Allowable Medication Categories.

Only immunomodulatory medication used to treat SLE will be included in summary tables of immunomodulatory medication usage (with the exception of the concomitant medication summaries which will include all medications). These are identified as those with a medication type of treatment for SLE (SDTM.CM.CMCAT = ‘SYSTEMIC LUPUS ERYTHEMATOSUS’).

It will be determined whether immunomodulatory agents are being received at any given reference date by using medication start and stop dates as follows:

- Start date and stop date are prior to reference date → subject is not on immunomodulatory agents
- Start date on or before date and stop date on or after reference date → subject is on immunomodulatory agents
- Start date on or before reference date, stop date is missing and medication is ongoing → subject is on immunomodulatory agents

Status of immunomodulatory medication is assessed at the following dates (i.e. these are the reference dates for the above derivation):

- Baseline
- Treatment completion date in treatment completers (Section [9.5.7](#))

It is also assessed for shift tables from baseline to:

- Treatment completion date (treatment completers)
- Study agent discontinuation date (subjects who prematurely discontinued study agent)

9.5.18. Baseline Allowable SLE Medications

It will be determined whether medications defined in [Appendix 3](#): SLE Allowable Medication Categories, with the exception of steroids, are being received at baseline by using medication start and stop dates as follows:

- Start date and stop date are prior to Day 1 → medication not taken at baseline
- Start date on or before Day 1 and stop date on or after Day 1 → medication is taken at baseline

- Start date on or before Day 1, stop date is missing and medication is ongoing → medication is taken at baseline

For steroids, baseline medication will be identified as that taken in the 7 days up to but not including Day 1 as described in Section 9.5.16.1.

9.5.19. SLICC/ACR Scoring

- For a given SLICC assessment, if any item(s) is missing, the entire assessment is excluded from summaries and analyses. The only exception to this is if the missing item has previously been scored with damage, in which case damage will be carried forward as detailed below.
- The SLICC/ACR Damage Index (see [Appendix 5: SLICC/ACR Damage Index](#)) increases over time. Once a subject meets the criteria for positive scoring of an item, that item should always be marked as present, even if the subject subsequently recovered. This includes baseline assessment.
- In the event the SLICC/ACR Damage Index is scored inconsistently (a decrease at Week 52 relative to baseline has occurred) and the data are unable to be queried and/or corrected, the baseline will be carried forward at the item level for the SLICC/ACR Damage Index questions, i.e. worst observation carried forward (WOCF). These carried forward values will then be used to calculate the total score which will be the value summarized and displayed for reporting. Within the renal domain, damage scored on the first two items (estimated glomerular filtration rate <50%, proteinuria >3.5 gm/24hours) should only be carried forward to Week 52 if the third item (end stage renal disease) has not been scored at Week 52. The reason for this is that scores on the first two items can decrease but only if the third item is then scored.
- Worsening is defined as an increase from baseline in SLICC/ACR Damage Index score (post-baseline visit score – baseline score) >0.
Note: SLICC/ACR is collected only at baseline and Week 52 (in subjects who do not withdraw from the study). It is not collected at the time of IP and or study withdrawal (where applicable) for potential imputation (i.e. carry forward) at Week 52 (see Section [12.2.3](#) for details).

10. STUDY POPULATION

The ITT population will be used to summarize the study population data and data will be presented by treatment and for all subjects combined, unless otherwise specified.

10.1. Disposition of Subjects

The number and percentage of subjects randomized by site will be grouped by country and summarized overall and by treatment group using the Randomized population.

Using the Randomized population, the number of subjects in each population (Randomized, ITT, As-Treated) will be summarized overall and by treatment group.

The database did not include all subjects screened for study participation or the number excluded before randomization. Therefore, screening data (including reason for screen failure) will not be summarized or included in the CSR submission datasets since it is not part of the database.

Using the ITT population, an overall summary of subject disposition will be presented with the following included:

- The number and percentage of subjects who completed IP.
 - The number and percentage of subjects who completed the study.
 - The number and percentage of subjects who withdrew from the study
- The number and percentage of subjects who withdrew early from IP.
 - The number and percentage of subjects who completed the study.
 - The number and percentage of subjects who withdrew from the study.
- The number and percentage of subjects who withdrew from the study on the same date as study agent discontinuation.
- The number and percentage of subjects who withdrew from the study at a later date than study agent discontinuation.

Further summaries of the ITT population will be produced of subject years' follow-up on-treatment, off-treatment and missing. This will also be given as a percentage of the total possible subject years. Summary statistics will be presented for each category of follow-up: total possible, on-treatment, off-treatment and missing. The summary will be provided for the mortality and malignancy data and all other data separately as the follow-up time differs (except for on-treatment follow-up time which is the same for mortality and malignancy and other data).

Using the ITT population, the subject's study completion status will be assessed to evaluate percentages of withdrawals from study by treatment group as well as the reasons for withdrawal from study. The number and percentage of subjects who completed through Week 52 and who withdrew, including reasons for withdrawal, will be displayed by treatment group and overall. Additionally, the cumulative number and percentage of subjects who withdrew by study visit, derived using visit windows defined in Section 9.5.3, will be displayed by treatment group and overall. A Kaplan-Meier plot of time to study withdrawal will be generated to evaluate the pattern of dropouts over time. Subjects who complete through Week 52 will be censored at the study completion date. The Kaplan-Meier plot will be truncated at Week 52.

Using the ITT population, the subject's IP completion status will be assessed to evaluate percentages of IP withdrawals by treatment group as well as the reasons for IP withdrawal. The number and percentage of subjects who completed IP through Week 48 and who withdrew, including reasons for IP withdrawal, will be displayed by treatment group and overall. Additionally, the cumulative number and percentage of subjects who withdrew from IP by study visit, derived using visit windows defined in Section 9.5.3, will be displayed by treatment group and overall. A Kaplan-Meier plot of time to study treatment withdrawal will be generated to evaluate the pattern of dropouts over time. Subjects who complete IP through Week 48 will be censored at the study treatment

completion date and for subjects who discontinue IP prematurely, the study treatment discontinuation date will be used as the discontinuation date. The Kaplan-Meier plot will be truncated at Week 52.

The number and percentage of subjects who deviated from the inclusion or exclusion criteria will be displayed by treatment group and overall. A listing of subjects who had a deviation from the inclusion or exclusion criteria will be provided.

A listing of subject disposition will be provided showing their completion status and whether they are included in each population. Subjects who are randomized but do not receive any study agent will be identified in this listing. A listing of subjects who withdrew from the study, including reason for and time to withdrawal will also be provided. An additional listing will be provided of subjects who withdrew from IP, including reason and time to withdrawal. Subjects for whom the treatment blind was broken during the study will be listed. A listing of planned and actual treatment arms will be provided. Subjects excluded from any population will be listed.

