6.3 Treatment Period

Subjects will be evaluated at the study site for the scheduled study visits outlined in the Study Calendar (Table 6-1). On Day 0, the subject will be randomized and receive the first dose of study agent. Subjects will be dosed at Week 2, Week 4 and approximately every 28 days (calculated from the Day 0 dose) thereafter through Week 48. The final treatment period evaluation for the study will occur at Week 52. Time windows are defined as ± 3 days for visits at Week 2 and Week 4, and ± 7 days for visits from Week 8 through Week 52. All study visits should occur within the visit window of the scheduled study visit. In rare circumstances, when the scheduled visit cannot be done within the visit window the Medical Monitor may be contacted for advice. Similarly, while all assessments for a dosing visit should be performed same day, in rare circumstances, an investigator may be permitted to conduct the assessments over two consecutive days so long as the infusion of the study agent is performed on the second day and after all other assessments.

All subjects who do not withdraw consent to participate in the first year monthly study visits and regardless of whether they continue to receive study agent will be followed on-study through Week 52 and annually for Years 2 through 5 (Week 260). All subjects will have a follow-up visit performed approximately 4 weeks after the last dose of study agent. In the event that a subject withdraws consent to participate in the first year monthly study visits, an attempt should be made at the time of consent withdrawal to obtain consent to contact the subject at Week 52 and annually for Years 2 through 5 (Week 260) to assess mortality and malignancy (including NMSC).

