6.5 Discontinuation of Study Agent

Subjects will be free to discontinue study agent treatment at any time, for any reason, or the investigator may discontinue study agent treatment, if necessary, to protect the subject's health (see reasons for study agent discontinuation below). Subjects who discontinue study agent after receiving at least 1 dose of study agent will not be replaced. Subjects who discontinue study agent will continue to be followed on-study through Week 52 (regardless of changes in

background medications) and annually for Years 2 through 5 (Week 260) according to the schedules outlined in [Table 6-1](#). All subjects will have a follow-up visit performed approximately 4 weeks after the last dose of study agent (i.e., the follow-up visit is Week 52 for a subject who completes all dosing visits, and the follow-up visit is the next scheduled visit for a subject who discontinues study agent).

Subjects may have study agent discontinued for any of the following reasons:

- At the investigator's discretion.
- Requires:
 - Other investigational agents.
 - Anti-TNF therapy (eg, adalimumab, etanercept, infliximab).
 - Other biologicals (eg, commercial belimumab, rituximab, abatacept, interleukin-1 receptor antagonist [anakinra]).
 - Live vaccines.
- Lost to follow-up.

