9.1.1. Treatment Period (to Week 52)

Subjects will receive IP through Week 48 with a final treatment period in clinic visit conducted at Week 52. Subjects who discontinue IP prior to Week 48 will have a follow-up in clinic visit performed approximately 4 weeks after the last dose of IP.

Per protocol, subjects may withdraw from IP during Year 1 and continue on study, or may withdraw from Year 1 study visits and consent to a Week 52 follow up. As a result, the time ‘on treatment’ versus the time ‘on study’ will differ for some subjects. Therefore, 2 analysis periods have been defined as the ‘On-Treatment’ and ‘On-Study’ periods. Further detail below.

The primary analysis summaries of Mortality, AESIs and SAEs will be performed using the ‘On-Treatment’ Period (defined in the table below).

Supportive summaries of the primary analysis will be performed using the ‘On-Study’ Period (includes on and off treatment data to Week 52).

For subjects who withdraw and re consent for a Week 52 assessment only mortality and malignancy are assessed at Week 52, whereas all other endpoints will be assessed only up until the time of withdrawal. Therefore, in this case follow-up for mortality and malignancy will be longer than for other assessments.

Study Period	Definition
Pre-Treatment	Date < Study Treatment Start Date
On-Study to Week 52	
All data except Mortality and Malignancy events:
 
Study Treatment Start Date ≤ Date ≤ minimum (Date of Death, maximum (Study Withdrawal or Completion Date (DSSTDT), Study Treatment Stop Date + 28 Days))
 
Mortality and all Malignancy events including NMSC (see Section 9.5.12 for definitions of mortality and malignancy events):
 
 • Alive or Lost to Follow Up at Week 52 Follow-Up: Study Treatment Start Date ≤ Date ≤ minimum (Last Known to be Alive Date, Study Treatment Start date + 371) • Dead at Week 52 Follow-Up: Study Treatment Start Date ≤ Date ≤ Date of Death • Week 52 follow-up missing: Study Treatment Start Date ≤ Date ≤ minimum (Date of Death, maximum (Study Withdrawal or Completion Date (DSSTDT), Study Treatment Stop Date + 28 Days)) 
Note: If the derived on-treatment period (i.e. study treatment stop date + 28 days) ends later than the derived on-study to Week 52 period, the derived on-study period will be updated such that it ends in line with the derived on-treatment period.

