9.5.3. Analysis Visit and Analysis Visit Number

Where applicable, the data are summarized per the planned visit assignment in the data. The visit windows below will be used to assign events to scheduled visits for tabular summaries of time to withdrawal from study, time to premature withdrawal from IP by clinical visit, cumulative time to mortality (On-Treatment Period) and cumulative time to mortality (On-Study Period).

Analysis Visit	Analysis Visit Number	Target Study Day ¹	Interval Start Day	Interval End Day
Screening	10	-30	Na	Na
Treatment Period visits:				
Baseline	25	1	Na	Na
Week 2	30	15	1	15
Week 4	40	29	16	29
Week 8	50	57	30	57
Week 12	60	85	58	85
Week 16	70	113	86	113
Week 20	80	141	114	141
Week 24	90	169	142	169
Week 28	100	197	170	197
Week 32	110	225	198	225
Week 36	120	253	226	253
Week 40	130	281	254	281
Week 44	140	309	282	309
Week 48	150	337	310	337
Week 52	160	365	338	[2]

¹Study Day with Baseline/Treatment Start Date as Day 1.

[2] Any events on or after Day 338 will be assigned to Week 52

9.5.4. Subject Years of Follow-Up to Week 52

Start and end dates for study periods are defined in Section 9.1. For calculation of exposure adjusted incidence rates (during the on-treatment period) and study follow-up adjusted incidence rates (during the on-study period), the following will be derived (in years) for each subject. Additionally, for summaries of subject follow-up time, the off-treatment, missing and total possible follow-up will be derived in years.

Note: The On-Study (to Week 52) terminology reflects the intended duration of follow-up for mortality and AESIs during the main study (i.e. 52 weeks). Some subjects will have less than 52 weeks of follow-up (e.g. where the subject has died or withdrawn from the study). The terminology ‘follow-up’ has been used to describe the time periods during which subjects are followed up for event assessment during the main 1-year study and does not refer to the post-treatment follow-up period in Years 2-5 (described in Section 9.1.2).

On-Treatment Follow-Up: Mortality and Malignancy and Other Data

$[(\text{End Date for On-Treatment Period} - \text{Study Treatment Start Date}) + 1]/365.25$

On-Study Follow-Up (to Week 52): Mortality and Malignancy

$[(\text{End Date of On-Study Period for Assessment of Mortality and Malignancy (to Week 52)} - \text{Study Treatment Start Date}) + 1]/365.25$

On-Study Follow-Up (to Week 52): Other Data

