9.5.7. Treatment Completer

A “treatment completer” is defined as a subject who does not discontinue study agent prematurely. Treatment completion date or treatment discontinuation date is defined using the date from SDTM.DS where DSSCAT='STUDY TREATMENT'. Treatment completion date is assigned for subjects who completed study treatment (DSDECOD='COMPLETED') and study treatment discontinuation date is assigned for subjects who did not complete study treatment (DSDECOD not missing and not equal 'COMPLETED').

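### The Kaplan-Meier plot of time to study treatment withdrawal censors completers at about Week 48 but runs to Week 52, so any late-dated discontinuation pulls its tail down

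*SAP*

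**What the plan says.** The rules for this plot are in the Week 52 RAP, Section 10.1, in the paragraph on IP completion status:

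- Completers: "Subjects who complete IP through Week 48 will be censored at the study treatment" completion date.
- Premature discontinuers are the events, and the sentence continues: "completion date and for subjects who discontinue IP prematurely, the study treatment discontinuation date will be used as the discontinuation date".
- End of the curve: "The Kaplan-Meier plot will be truncated at Week 52".

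Related text:

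- Week 52 RAP 9.1.1 separates last dose and last visit: "Subjects will receive IP through Week 48 with a final treatment period in clinic visit conducted at Week 52".
- Protocol 6.3 sets the visit window at plus or minus "7 days for visits from Week 8 through Week 52".
- Week 52 RAP 9.5.7 defines a treatment completer as someone who does not stop study agent early, and takes both dates from the disposition record: "Treatment completion date or treatment discontinuation date is defined using the date from SDTM.DS where DSSCAT='STUDY TREATMENT".
- Protocol 6.5: "Subjects who discontinue study agent will continue to be followed on-study through Week 52". A discontinuation can therefore be recorded after Week 48.
- Week 52 RAP 9.5.3, in the window table that also serves the by-visit summary of IP withdrawal: "Any events on or after Day 338 will be assigned to Week 52".

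The paragraph also asks for the number and percentage completing and withdrawing from IP, and the cumulative percentage withdrawn by visit. It does not ask for numbers at risk on this plot, whereas Section 11.1.1 does for the mortality curve.

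**The concern.** Kaplan-Meier censoring treats a subject who leaves the risk set as someone who could still have the event later. A treatment completer cannot: by the definition in 9.5.7 the outcome is already known to be no premature discontinuation. Censoring completers at completion therefore discards known information and shrinks the denominator to almost nothing for about the last three weeks of the plot. Each discontinuation dated in that stretch then produces a step far larger than its true share of the arm.

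At stake is how the figure reads. Its stated purpose is to show dropout from treatment over time by arm. Two arms with the same completion proportion could end at very different heights because of one or two late dates, and the figure could disagree with the correct cumulative withdrawal table specified in the same paragraph.

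**Working it through.** The plan gives no figure for this plot, so there is none to reproduce.

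**Inputs from the documents**

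- Subjects per arm: about 2,000 (4,000 randomized 1:1; Week 52 RAP, Section 3).
- Week 48 target: study Day 337 (RAP 9.5.3). With the 7-day window, in-window completion falls on 337 - 7 = 330 to 337 + 7 = 344.
- End of plot: Week 52, Day 365.

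**Assumptions, because the documents give no value**

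- 80% complete IP (1,600 of 2,000). Runs at 70% and 90% show the same pattern.
- Completion is dated at the Week 48 visit, with 0, 0.5, 2 or 5% of completers (0, 8, 32 or 80 subjects) dated on Days 345-365.
- The number and timing of late discontinuations vary as shown below.

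**Formula.** S(t) is the product, over event days up to t, of (1 - d/n), where d is the number of discontinuations that day and n the number still at risk.

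**One late discontinuation, by hand.** There are 400 discontinuations, 399 of them before completers start to leave, so S(344) = 1,601/2,000 = 0.8005. If r completers remain at risk on the day of the last one, the curve becomes 0.8005 × r/(r + 1):

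| Completers still at risk (r) | Curve after the event |
|---|---|
| 1,600 (none censored yet) | 80.0% |
| 80 | 79.1% |
| 32 | 77.6% |
| 8 | 71.2% |
| 1 | 40.0% |
| 0 | 0% |

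The true value is 80.0% in every row.

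**Simulation.** Mean Day 365 value, 80% completing, late discontinuations spread over Days 345-365:

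| Completers dated after Day 344 | 1 late | 3 late | 5 late | 10 late |
|---|---|---|---|---|
| 0 | 0% | 0% | 0% | 0% |
| 0.5% (8) | 55% | 36% | 18% | 9% |
| 2% (32) | 72% | 59% | 49% | 29% |
| 5% (80) | 76% | 70% | 65% | 53% |

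Other timings, same arm:

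- Late dates spread over Days 338-365: median about 42% (ten late, 2% of completers dated late) and about 75% (three late, 5% dated late).
- All late dates on Days 338-344: a mean of 79% to 72% for 3 to 20 of them.
- No late discontinuation: 80%.
- Completion recorded at about Week 52, with 1 to 10 discontinuations on Days 338-365: 80%.

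**After the change.** With completers kept at risk to Day 365 nobody is censored earlier, so the product telescopes. In the one-event example, 1,601/2,000 × 1,600/1,601 = 1,600/2,000 = 80.0%. Simulated values are exactly 70%, 80% and 90% at those completion proportions, with 0, 5 or 20 late discontinuations. Ending the plot at Day 329 gives 80.0-81.0% when 80% complete, because up to 20 later discontinuations (20/2,000 = 1%) are not yet counted.

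**The case against.** The strongest reply is that the drop needs two things the documents do not establish.

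First, completion must be dated at about Week 48. Section 9.5.7 takes the date from the disposition record, while 9.1.1 separately defines the treatment stop date from the final infusion. The two need not coincide, and if sites record completion at the Week 52 visit the artefact disappears. This stands as a condition, although completing IP through Week 48 points to the earlier date.

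Second, some discontinuations must be dated after most completers have left. A reader might take the Day 338 footnote in 9.5.3 as showing that the plan expects them. It does not. It is the open-ended last bin of a table shared by four summaries, and deaths or study withdrawals alone would require such a bin. It permits late IP withdrawals without predicting them, and it opens while many completers are still at risk.

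Two further inferences should be resisted. One is that the on-treatment safety comparison is distorted. Section 11.1.1 uses percentages and subject-year rates, not this curve. The disposition tables and the listing of IP withdrawals are also unaffected, and the plot is not among the headline results in 16.3. The other is that the study-withdrawal plot shares the fault. Its completers are censored at about Week 52, where it ends; with 5 to 20 withdrawals on Days 358-365 it reads 79.8-79.9% against a true 80%.

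The mock shells are a separate document and may already require numbers at risk. That would warn the reader but would not correct the curve.

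**Conclusion.** The censoring rule is wrong for this quantity as written: it removes subjects whose outcome is known and leaves the last weeks of the curve resting on very few. With 2,000 per arm and 80% completing, the Day 365 value can lie anywhere from 80% (no artefact) through about 42-75% to 0%, depending on recorded dates that the documents do not give. A reader might infer that the curve will fall to zero. That holds only if at least one discontinuation is dated after the last completer is censored and by Day 365, which the documents do not establish.

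The consequence is limited to the tail of one descriptive disposition figure, which may then disagree with the correct cumulative IP-withdrawal table. No safety or efficacy estimate changes. It is a minor point, worth correcting because the correction is nearly free.

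**What to change.** In Section 10.1 of the Week 52 RAP, for the plot of time to study treatment withdrawal only, keep subjects who complete IP at risk to the truncation day by censoring them at Day 365. The curve then equals 1 minus the cumulative proportion discontinued and agrees with the by-visit table. Alternatively, end the plot at Day 329, before completers can leave within the visit window. In either case, show numbers at risk by arm. Leave the study-withdrawal plot as it is.

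The cost is one sentence of RAP wording and one programming line, with no new data. The Years 2 to 5 RAP states that the Week 52 analyses have already been reported. The practical step is therefore to check whether any discontinuation was dated after most completers had left, and if so to regenerate or footnote the figure.
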